7. STUDY PROCEDURES

The assessments and procedures that will be conducted during this study are summarized in [Table 1](#).

7.1. Screening

Potential study patients will be examined before the start of the study to determine their eligibility for participation. Informed consent must be obtained and signed before initiation of screening activities. The following screening procedures and assessments must be performed within 2 weeks before study enrollment and initiation of the Placebo Lead-in Period.

- Obtain written informed consent/assent (if appropriate).
- Review of inclusion and exclusion assessment.
- Record medical history and demographics.
- Perform a complete physical examination.
- Clinical laboratory tests (clinical chemistry, hematology, and urinalysis).
- Perform resting 12-lead ECG.
- Urine drug screen (drugs of abuse including THC).
- Record vital signs (seated blood pressure, pulse rate, temperature, and respiration rate).
- Urine dipstick pregnancy test (all female patients of childbearing potential).
- Record weight.
- Complete the HQ-CT.
- Review concomitant medications.
- Review AEs.

7.2. Placebo Lead-In Period

7.2.1. Visit 2 (Week -2)

Patients who complete all Screening assessments and meet the study entry criteria will be assigned to the Placebo Lead-In Period. The following procedures and assessments will be performed at Visit 2:

- Perform a complete physical examination.
- Record vital signs (seated blood pressure, pulse rate, temperature, and respiration rate).
- Dispense study medication.
- Record weight.
- Complete the HQ-CT.
- Review concomitant medications.

- Review AEs.

7.3. Titration Period

7.3.1. Baseline (Visit 3, Day 1)

At Visit 3 (Baseline), eligible patients will be randomized and enter a 1 week Titration Period.

The following procedures and assessments will be performed at Baseline (Visit 3):

- Randomization.
- Perform a complete physical examination.
- Record vital signs (seated blood pressure, pulse rate, temperature, and respiration rate).
- Collect/review/dispense study medication.
- Record weight.
- Complete the HQ-CT.
- Complete the TFEQ-R18.
- Complete the PROMIS Life Satisfaction and Positive Affect questionnaires.
- Complete the PROMIS Physical Activity and Fatigue questionnaires.
- Complete PGI-S.
- Perform DEXA scan.
- Complete the C-SSRS.
- Take PK sample blood draw.
- Review concomitant medications.
- Review AEs.

Titration will begin at 20 mg/kg/day divided into twice daily dose with standard meal for 3 days. If the 20 mg/kg/day dose of study medication has been well tolerated, patient will increase the dose of study medication by 1 dose level to 30 mg/kg/day divided into twice daily dose with standard meal for 3 days. If the 30 mg/kg/day dose of study medication has been well-tolerated, patient will up titrate to the maximum dose of 40 mg/kg/day and start the 12-week Maintenance Period.

If the initial 20 mg/kg/day or the 30/mg/kg/day doses of study medication were NOT well-tolerated, the drug will be discontinued and the patient withdrawn from the study.

The Investigator or designee will call on Day 3 and Day 6 to determine if the patient's dose may be titrated to the next dose level.

7.3.2. Visit 4 (Day 7)

The following procedures and assessments will be performed at Visit 4:

- Perform a complete physical examination.

- Record vital signs (seated blood pressure, pulse rate, temperature, and respiration rate).
- Collect/review/dispense study medication.
- Record weight.
- Complete the HQ-CT.
- Review concomitant medications.
- Review AEs.

7.4. Maintenance Period

Patients will be administered 40 mg/kg/day or matching placebo, divided twice daily for 12 weeks. If unacceptable adverse reactions are observed at 40 mg/kg/day, treatment may be decreased to 30 mg/kg/day. If the lower dose is not tolerated, the drug will be discontinued and the patient will be withdrawn from the study.

7.4.1. Visit 4-9 (Week 3 to 11)

The following procedures and assessments will be performed at each of Visits 5-9 (unless otherwise specified) during this period:

- Perform a complete physical examination.
- Record vital signs (seated blood pressure, pulse rate, temperature, and respiration rate).
- Perform resting 12-lead ECG (Visit 6/Week 5 and Visit 8/Week 9 only).
- Collect/review/dispense study medication.
- Record weight.
- Complete the HQ-CT.
- Complete the TFEQ-R18 (Visit 5/Week 3 and Visit 8/Week 9).
- Complete the PROMIS Life Satisfaction and Positive Affect questionnaires (Visit 5/Week 3 and Visit 8/Week 9).
- Complete the PROMIS Physical Activity and Fatigue questionnaires (Visit 5/Week 3 and Visit 8/Week 9).
- Complete PGI-C (Visit 5/Week 3 and Visit 8/Week 9).
- CBC assessment (Visit 5/Week 3).
- PK sample blood draws (Visit 6/Week 5 and Visit 8/Week 9).
- Review concomitant medications.
- Review AEs.

7.4.2. Visit 10 (Week 13; Study Completion) or Early Withdrawal

The following procedures and assessments will be performed at Visit 10 or following patient withdrawal:

- Perform a complete physical examination.
- Record vital signs (seated blood pressure, pulse rate, temperature, and respiration rate).
- 12-lead ECG.
- Clinical laboratory tests (clinical chemistry, hematology, and urinalysis).
- Urine dipstick pregnancy test (all female patients of childbearing potential).
- Collect/review/dispense study medication.
- Record weight.
- Complete the HQ-CT
- Complete the TFEQ-R18.
- Complete the PROMIS Life Satisfaction and Positive Affect questionnaires (Visit 5/Week 3 and Visit 8/Week 9).
- Complete the PROMIS Physical Activity and Fatigue questionnaires (Visit 5/Week 3 and Visit 8/Week 9).
- Complete PGI-C.
- DEXA scan.
- Complete the C-SSRS.
- PK sample blood draw.
- Review concomitant medications.
- Review AEs.

7.5. Taper Period

After completion of the study, patients will be offered an opportunity to enroll in an open-label, long-term safety study. Patients who choose to enroll in the long-term safety study will not have a follow-up visit. Patients who do not elect to enroll in the long-term safety study will be titrated off the study drug over 7 days according to the following schedule: 40 mg/kg/day to 30 mg/kg/day for 3 days, to 20 mg/kg/day for 3 days, and then discontinue the drug on Day 7.

7.6. Follow-Up Period

7.6.1. Visit 11 (Week 15)

For patients who do not choose to enroll in the long-term safety study, the following assessments will be performed:

- Collect/review study medication.
- Review concomitant medications.
- Review AEs.

Patients who enroll in the long-term safety study do not complete the Follow-Up Visit.

8. STATISTICS

The detailed descriptions of statistical analysis methods and data conventions will be in a separate document, the Statistical Analysis Plan (SAP). Any post-hoc analyses will be identified in the final clinical study report. This section presents general information about statistical considerations and concepts such as randomization, statistical power, and sample size. There will also be a brief discussion on analysis methodology and data conventions.

8.1. Efficacy Endpoints

8.1.1. Primary Efficacy Endpoint

- Change in the total score of the HQ-CT from Baseline (defined as the score after the Placebo Lead-In Period) through Study Completion (Week 13/Early Withdrawal).

8.1.2. Secondary Efficacy Endpoints

The secondary efficacy endpoints in this study are:

- Change in total body-weight from Baseline through Study Completion/Early Withdrawal.
- Responder rate (responder is defined as 6-point decrease on the HQ-CT from Baseline through Study Completion).
- Change in Patient Global Impression of Change and Severity (PGI-C).
- Change in the TFEQ-R18 from Baseline through Study Completion/Early Withdrawal.
- Change in Quality of Life (PROMIS Life Satisfaction and Positive Affect questionnaires) from Baseline through Study Completion/Early Withdrawal.
- Change in physical activity (PROMIS Physical Activity and Fatigue questionnaires) from Baseline through Study Completion/Early Withdrawal.

8.1.3. Exploratory Efficacy Endpoint

- Change in body composition from Baseline to Study Completion/Early Withdrawal as measured by DEXA.

8.2. Safety Endpoints

The safety endpoints are treatment-emergent AEs (TEAEs), clinical laboratory assessments, vital signs (blood pressure, pulse rate, respiration rate, and temperature), 12-lead ECGs, physical examination assessments, pregnancy screens, urine drug screen (including THC), medical history, and prior and concomitant medications.

8.3. Pharmacokinetic Endpoints

The secondary efficacy endpoints in this study are:

- Trough concentrations (C_{trough}) of CBD and metabolite 7-OH-CBD will be used to assess the exposure-response relationship.

8.4. Sample Size Determination

A total of 30 patients per treatment group will provide more than 85% power with an alpha of 0.05, for a difference in the HQ-CT from Baseline to Week 13 of 5 points with standard deviation of 6. Assuming a 20% drop out rate, approximately 66 patients (33 patients per arm) will be randomized to achieve 60 (30 patients/arm) completers.

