
Reference therapy, dosages and modes of administration: Matching placebo, divided into twice daily doses with standard meal, manufactured for and supplied by Insys Development Company, Inc.

Criteria for evaluation:
 
Efficacy
 
Primary efficacy endpoint:
 
 • Change in the total score of the HQ-CT from Baseline (defined as the score after the 2-week Placebo Lead-In) through Study Completion (Week 13/Early Withdrawal). 
Secondary efficacy endpoints:
 
 • Change in total body-weight from Baseline through Study Completion/Early Withdrawal. • Responder rate (responder is defined as 6-point decrease on the HQ-CT) from Baseline through Study Completion). • Change in Patient Global Impression of Change (PGI-C). • Change in the TFEQ-R18 from Baseline through Study Completion/Early Withdrawal. • Change in the Quality of Life (PROMIS Life Satisfaction and Positive Affect short form pediatric questionnaires) from Baseline through Study Completion/Early Withdrawal. • Change in physical activity (PROMIS Physical Activity and Fatigue pediatric questionnaires) from Baseline through Study Completion/Early Withdrawal. 
Exploratory efficacy endpoint:
 
 • Change in body composition and bone mineral density from Baseline to Study Completion/Early Withdrawal as measured by DEXA. 
Safety

The safety endpoints are treatment-emergent AEs (TEAEs), clinical laboratory assessments, vital signs (blood pressure, pulse rate, respiration rate, and temperature), 12-lead ECGs, physical examination assessments, pregnancy screens, urine drug screen (including THC), medical history, and prior and concomitant medications.

Pharmacokinetic

- Trough concentrations (C_{trough}) of cannabidiol (CBD) and metabolite 7-hydroxy-CBD (7-OH CBD) will be used to assess the exposure-response relationship.

Statistical Methods:**Sample Size Calculation**

A total of 30 patients per treatment group will provide more than 85% power with an alpha of 0.05, for a difference in the HQ-CT from Baseline to Week 13 of 5 points with standard deviation of 6. Assuming a 20% drop out rate, approximately 66 patients (33 patients per arm) will be randomized to achieve 60 (30 patients/arm) completers.

Analysis Populations

Statistical analyses will be conducted on the following populations:

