3.3. Removal of Patients from Therapy or Assessment

Patients will be allowed to discontinue their participation in the study at any time for any reason (withdrawal of consent). Furthermore, participation in this clinical study may be discontinued by the Investigator or by the sponsor for any of the following reasons:

- Intolerable side effects of the study product.

- Changes in medical status or medical condition of the patient such that the Investigator believes that patient safety will be compromised or that it would be in the best interest of the patient to stop treatment.
- Pregnancy.
- Relevant non-compliance with the protocol.
- Any use of marijuana, confirmed by a positive drug screen for THC.

In the event of a patient's withdrawal, the Investigator will promptly notify the sponsor. Every effort will be made to complete the end-of-study assessments.

Should any patient choose to withdraw early from the study, they will be advised of the safety precautions to be taken and will be followed until resolution of any AE or until the unresolved AEs are judged by the investigator to have stabilized.

Patients who are withdrawn from the study may be replaced at the discretion of the Sponsor.

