4.3. Method of Assigning Patients to Treatment Groups

Following the 2-week Placebo Lead-In Period of the study, patients will be randomized in a 1:1 ratio, using a web-based randomization system. The randomization will be stratified according to growth hormone treatment (yes/no).

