8.6.3.1. Primary Efficacy Analysis

The primary outcome variable for the study is the change in total score of the HQ-CT from Baseline through Study Completion/Early Withdrawal. The primary efficacy endpoint will be tested using a 2-sided type I error rate of 0.05.

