2.3 Sample Size and Power

A total of 30 patients per treatment group will provide at least 85% power with an alpha of 0.05, to detect a difference in the change in HQ-CT from Baseline to Week 13 of 5 points with a standard deviation of 6. Assuming a 20% drop out rate, approximately 66 patients (33 patients per arm) will be randomized to achieve 60 (30 patients per arm) completers.

3. Efficacy and Safety Endpoints

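### 66 randomised with the stated 20% dropout gives about 53 completers, not 60, and completer power of about 84% rather than 89%

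*Protocol*

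**What the plan says.** The sample size statement appears three times: in the protocol synopsis (Sample Size Calculation), in protocol section 8.4 and in SAP section 2.3.

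- **Power.** The protocol says: "A total of 30 patients per treatment group will provide more than 85% power with an alpha of 0.05". The SAP has a slightly softer form: "A total of 30 patients per treatment group will provide at least 85% power with an alpha of 0.05".
- **Effect.** Protocol 8.4 takes the power "for a difference in the HQ-CT from Baseline to Week 13 of 5 points with standard deviation of 6".
- **Test.** Protocol 8.6.3.1: "The primary efficacy endpoint will be tested using a 2-sided type I error rate of 0.05".
- **Allocation.** Protocol 4.3: "patients will be randomized in a 1:1 ratio, using a web-based randomization system".
- **Dropout.** Protocol 8.4: "Assuming a 20% drop out rate, approximately 66 patients (33 patients per arm) will be randomized to achieve 60 (30 patients/arm) completers". SAP 2.3 repeats it: "Assuming a 20% drop out rate, approximately 66 patients (33 patients per arm) will be randomized to achieve 60 (30 patients per arm) completers".

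The synopsis paragraph on the planned number of patients also goes from 66 enrolled to 60 completing, but gives no dropout rate. Protocol 3.3 adds: "Patients who are withdrawn from the study may be replaced at the discretion of the Sponsor". No sample size statement refers to that provision. SAP section 8 records no changes to the planned analysis, so nothing later corrects the figures.

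**The concern.** One sentence gives a dropout rate, a number randomised and a number of completers. Any two of these fix the third, and the third figure given is not the one that follows.

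This matters because the power claim is made for 30 patients per arm, and the dropout sentence identifies those 30 as completers. If 20% is the real expectation, the trial as sized does not deliver them, and the power at the plan's own dropout rate is lower than at 30 per arm. If 60 completers is the real expectation, the dropout rate is overstated by a factor of about two. A reader cannot tell which was planned.

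**Working it through.** **Inputs.** Difference 5 points and SD 6 (protocol 8.4, SAP 2.3); two-sided alpha 0.05 (protocol 8.6.3.1); 1:1 allocation (protocol 4.3); 20% dropout, 66 randomised and 60 completers (protocol 8.4, synopsis, SAP 2.3).

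**Step 1: reproduce the stated power at 30 per arm.** The noncentrality is difference / (SD × √(2/n)) = 5 / (6 × √(2/30)) = 3.23.

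- Two-sample t-test, 58 degrees of freedom: 88.8%.
- Normal approximation, Φ(3.23 − 1.96): 89.8%.

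Both exceed 85%, so the power claim for 30 per arm is sound.

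**Step 2: try to reproduce 66.**

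- Correct inflation, N/(1 − d): 60/0.80 = 75, or 76 with equal arms (38 each).
- The common shortcut, N × (1 + d): 60 × 1.20 = 72.

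Neither gives 66. What does give 66 is 60 × 1.10, an inflation of 10%.

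**Step 3: what each pair of figures implies for the third.**

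| Held fixed | Implied third figure | Plan states |
|---|---|---|
| 66 randomised, 20% dropout | 66 × 0.80 = 52.8 completers (26.4 per arm) | 60 |
| 60 completers, 20% dropout | 60/0.80 = 75 randomised | 66 |
| 66 randomised, 60 completers | 1 − 60/66 = 9.1% dropout | 20% |

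The completer shortfall at 20% is about 7 of 60, or 12%.

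**Step 4: power at the completers that 20% dropout leaves.**

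| Completers per arm | t-test | Normal approximation |
|---|---|---|
| 30 | 88.8% | 89.8% |
| 27 | 85.2% | 86.5% |
| 26.4 | 84.4% | 85.7% |
| 26 | 83.8% | 85.2% |

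From 30 to 26.4 per arm the loss is 4.4 points by the t-test and 4.1 by the normal approximation (89.8 − 85.7).

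**The case against.** Five points can be made for the plan.

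1. **The wrong figure may be the 20%.** The synopsis paragraph on planned numbers goes from 66 to 60 without a dropout rate, which fits a planned loss of about 9%. On that reading the trial keeps 30 per arm and 88.8% power. This is possible, and the documents do not settle it. It is one way of correcting the sentence, not a reason to leave it. Nor was dropout disregarded altogether, since 60 was raised by 10%.

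2. **Falling below 85% depends on the formula.** The documents name none. The t-test misses by 0.6 points at 26.4 per arm, the normal approximation stays above, and 27 completers per arm would satisfy both. This stands: the breach is marginal.

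3. **Completers are not the analysis set.** SAP 7.6.1 fits a mixed model for repeated measures to all randomised patients with a baseline and at least one later HQ-CT score. The score is taken at seven post-baseline visits, and the last of these is also the early withdrawal visit, so many dropouts contribute data. The model also adjusts for baseline. If 6 is the unadjusted SD of change (an assumption, as the documents do not say), a residual SD of 5.9 would bring t-test power at 26.4 per arm to 85.5%. This stands too: 84% is a conservative completer figure, not the power of the planned model. But the plan justifies its size by completers, and the model does not turn 53 of them into 60.

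4. **Withdrawn patients may be replaced** (protocol 3.3). Replacement is discretionary, is not part of the sample size argument, and would reach 60 only by randomising more than 66.

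5. **The count is only approximate.** That wording does not cover a gap of nine patients, 66 against 75.

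**Conclusion.** The sample size statement is wrong as written in all three places. That conclusion needs only division and no choice of power formula.

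The consequence for power is modest. If 20% dropout is what the sponsor expects, completer power is about 84% by the two-sided t-test instead of about 89%, just under the stated 85%; by the normal approximation it is just over. These figures assume a 5-point difference, SD 6, two-sided 0.05, equal arms and no contribution from dropouts. The last assumption makes them conservative for the analysis actually planned. If about 9% is the true expectation, power is unaffected and only the dropout figure is wrong.

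**What to change.** Keep 66 patients and correct the sentence identically in the protocol synopsis, protocol 8.4 and SAP 2.3, in one of two ways:

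- **(a) 20% is the expected dropout.** State that 66 randomised is expected to give about 53 completers (about 26 per arm), with about 84% power by a two-sided two-sample t-test. A note that the repeated-measures model also uses data from patients who leave early would be fair.
- **(b) 60 completers is the expectation.** State the dropout as about 9%. The figures of 66, 60 and more than 85% power then agree.

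Under (a), the synopsis paragraph on planned numbers must change too, because it also promises 60 completers. In either case, name the power formula, since the result lies so close to 85%.

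Holding both 20% and 60 completers would require 75 randomised (76 with equal arms). That changes recruitment and is not needed to repair the statement. Options (a) and (b) change wording only: no endpoint, analysis or recruitment target moves. The one cost is that (a) reports a slightly less favourable power.

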8.5. Analysis Populations

Statistical analysis will be done on the following populations:

- **Intent to Treat (ITT) Population:** The ITT Population will include all patients who were randomized. The ITT Population will be used for all efficacy analyses.
- **Safety Population:** The Safety Population will include all patients who were treated with at least one dose of the study drug. The Safety Population will be used for all safety assessments.

8.6. Statistical Analyses

8.6.1. Study Patients and Demographics

Analysis Treatment group will be defined by the modal dose of study drug (dose group the patient took for the longest period).

8.6.1.1. Disposition and Withdrawals

The numbers of patients randomized, completing, withdrawing, and reasons for withdrawal, will be tabulated overall and by treatment group. The number of patients in each analysis population will be reported.

8.6.1.2. Protocol Deviations

Protocol deviations will be identified and listed.

8.6.1.3. Demographics and Other Baseline Characteristics

Descriptive analyses will be conducted for the safety population.

Demographic and baseline characteristics (including sex, age, gender, ethnicity, race, and weight, and BMI) will be summarized by descriptive statistics. No formal statistical analyses will be performed. Medical history, clinical laboratory test results, and ECG assessments will be listed.

Prior and concomitant medications will be summarized by the number and percentage of patients taking each medication. They will also be classified by using the World Health Organization Drug Dictionary Anatomical Therapeutic Chemical classes and preferred terms.

8.6.2. Exposure and Compliance

The total exposure to study medication will be summarized by descriptive statistics by treatment group.

8.6.3. Efficacy Analyses

Statistical inference for the primary endpoint and for key secondary endpoints will be controlled at an overall family wise error rate (alpha) of 0.05, 2-sided. For continuous endpoints, number of observations, mean, standard deviation (SD), median, minimum and maximum will be presented as descriptive statistics. For inferential statistics, analysis of covariance (ANCOVA) with the baseline value and randomization strata (growth hormone treatment) as covariates will be used. For multiple values, a repeated measures analysis will be performed. For categorical endpoints, the number of observations, frequency counts and percentages will be presented as descriptive statistics, and Fisher's exact test will be used for inferential statistics.

8.6.3.1. Primary Efficacy Analysis

The primary outcome variable for the study is the change in total score of the HQ-CT from Baseline through Study Completion/Early Withdrawal. The primary efficacy endpoint will be tested using a 2-sided type I error rate of 0.05.

8.6.3.2. Secondary Efficacy Analysis

The secondary endpoints, which will be assessed inferentially, are change in total body-weight, response rate, PGI-C, TFEQ-R18, PROMIS Life Satisfaction and Positive Affect, PROMIS Physical Activity and Fatigue.

